# 1. JUSTIFICATION OF THE STUDY

Undernutrition and the prevention of its risk in elderly people in seniors's resident constitute a major public health issue. The diagnosis of undernutrition and its risk are systematically recommended in these structures where the food of the persons is a problem because often unsuited to their capacities of grip and consequently to their nutritional needs. One of the solutions to remedy this could be the food offer proposed by the "finger-food".

The FIFO (Finger-Food) study, with a monocentric and randomized design, aims to verify the hypothesis that "finger-food" would increase food intake in seniors's residents with prehension disorders and/or requiring feeding stimulation and/or assistance with meal preparation.

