### 2.1.3 Primary endpoint

Quantitative measurement of ingesta (caloric and protein intake), monthly between M-1 (before implementation of the "finger-food") and M6.

The assessment of nutritional intakes will be carried out on 3 consecutive days, by a dietician, for lunch and dinner, at a point in time between M-1 and M0 (i.e. before the implementation of the "eat-in" system), and then monthly.

This dietary assessment will be done by means of photos BEFORE/ AFTER the consumption of the meal, by the housekeepers. The photos will target the actual consumption of the meal compared to the proposed service. This tool is preferred to the food monitoring form, usually used in the seniors's residents, but which does not allow for a detailed analysis of the food consumed and the quantities per dish actually ingested by the residents.

Also, the environment of the meal will be photographed in order not to wrongly consider the possible food losses, notably food on the ground, as food contributions. The residents' faces will not be photographed.

Information on the taking of these photographs will be provided to the appropriate people in order to have an image quality that is conducive to analysis and to respect a certain homogeneity of distance in the taking of photographs and in the analysis that will result from them.

The same dietician will ensure the analysis of the photos and intakes to avoid bias.

The photos will be analyzed using a quantitative and qualitative approach:

Meal consumption: A global evaluation of the meal will be done according to whether the resident ate all of his meal, /4, half, /4 of his meal or nothing at all, while taking

into account the environment.

- Type of dish consumed (starter / main course: meat-fish-egg, vegetable-starch / dairy product / dessert).
- The caloric (in kilocalories) and protein (in grams) intakes of the meal trays will be calculated before distribution to the residents.
- The same calculations will be made after the meal has been consumed, taking into account the environment and what the resident has actually eaten. They will be compared to the amount of the proposed meal tray in order to take into account residents with a poor appetite for whom half portions are usually proposed.

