#### STEP 2 : M0 – M6

• M0 : Implementation of « hand-held » or traditional feeding depending on the randomization arm of the resident.

This step consists in setting up the "finger-food" vs traditional food according to randomization, on the 3 sites of the CHD Vendée, after information/training of the ad-hoc professionals (care services, catering).

The same manufacturing process is planned for all 3 sites.

The distribution of this offer will be ensured by the catering of each site to the services concerned (in individual, nominative trays). The temperature of the food will be adapted to allow consumption with the hands.

At the beginning of this stage (M0), each resident included in the arm with "finger-food" will receive the 2 main meals (lunch and dinner) in the form of finger foods. Those included in the arm without "finger-food" will have the food offer as usually proposed. Breakfast remains the same as usual.

2 types of "finger-food" are planned in the study, depending on the feeding abilities of each resident (normal texture or modified texture) :

- The "classic hand-eater" for residents who are able to eat with a normal texture but have praxis problems and/or physical handicaps.

The proposed food offer will allow to grasp with the fingers, the dishes presented in the form of reduced portions. A diversity of presentation types is planned: food cut into cubes, slices, or sticks (raw vegetables, fruits), meatballs, fish croquettes, surimi, flans, quiches, quenelles, fritters, toasts, terrines, cheese, yoghurt drinks, compote drinks, ice cream sticks, cookies... The composition in macronutrients and in particular the caloric and protein contributions, will be identical and preserved between the "classic" menu and the "classic eat-in" menu.

- The "smooth mixed feed" for residents who are unable to eat with a normal texture because they are edentulous and/or have oral pathologies and/or swallowing problems.

In this case, it will be the variation of the "mixed" meal in "eat-in" presentation, in the form of bites, whose consistency has been modified with the use of vegetable gelatins. They will be presented in the form of small portions that can be consumed in 1 to 2 bites. The composition in macronutrients and in particular the caloric and protein contributions, will be identical and preserved between the menu "usual mixed smooth" and the menu "eat hands mixed smooth".

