### Primary endpoint :

The evolution of caloric and protein intakes between inclusion and 6 months will be compared between the 2 groups by a Wilcoxon Mann-Whitney test.

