### 6.2.2 Statistical justification of the number of inclusions

To our knowledge, no clinical study has been carried out on the impact of "finger-food" in seniors's residents. Therefore, we have no data available that would allow us to make working hypotheses on its impact on the nutritional status of patients.

The purpose of this pilot study is therefore to collect preliminary data on the nutritional evolution of these patients.

No statistical calculations were performed. All residents of the 6 participating seniors's residents who met the inclusion criteria were included in the study.

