### 6.2.3 Expected level of statistical significance

The significance level is set at 5%.

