### 6.2.5 Consideration method for missing, unused or invalid data

The main criterion being the comparison of the evolution of the quantity of ingesta between the inclusion and the 6 months of follow-up, a missing value of these data will entail an imputation of this one by the worst value then, by the average of its group.

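### Do two primary intake measures, calories and protein, with one unsplit 5% level call for a multiplicity rule in this pilot?

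*Combined protocol and SAP*

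**What the plan says.** Section 2.1.3 defines the primary endpoint as "Quantitative measurement of ingesta (caloric and protein intake), monthly between M-1" and M6. The two parts have different units and are worked out separately: "The caloric (in kilocalories) and protein (in grams) intakes of the meal trays will be calculated before distribution to the residents", and again after the meal. No combined score is defined.

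Section 6.2.1 gives the primary analysis: "The evolution of caloric and protein intakes between inclusion and 6 months will be compared between the 2 groups", by a Wilcoxon Mann-Whitney test. Section 6.2.3 adds "The significance level is set at 5"%, with no split between measures and no statement that it is an overall level.

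Section 6.2.5, on missing data, speaks in the singular: "The main criterion being the comparison of the evolution of the quantity of ingesta" from inclusion to six months. It does not say how calories and protein make up that quantity.

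On the status of the study, section 6.2.2 says "The purpose of this pilot study is therefore to collect preliminary data" and reports that no sample size was calculated. The Summary, under expected results, leaves the framing of hypotheses to later projects with an impact study. Section 1, by contrast, says the trial "aims to verify the hypothesis that" finger-food would raise food intake.

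**The concern.** A Wilcoxon Mann-Whitney test compares one variable between two groups. With two variables and no composite, the natural reading is two tests, each judged at 5%. The plan gives no order of testing, no requirement that both succeed, no adjusted level and no single deciding measure.

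Two things could then go wrong. If the results disagree, the plan does not say whether the main objective has been met, and in an open study the deciding measure could be picked once the results are known. If a positive result on either measure were enough, the chance of at least one false positive would be higher than the 5% in section 6.2.3. For a trial that describes itself as verifying a hypothesis, that is a fair question to raise.

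**Working it through.** **The plan's own figure.** The only error rate in the documents is the 5% of section 6.2.3. It is a chosen level, not a derived one, so there is nothing to reproduce. It is correct for each test taken alone.

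**Inputs**
- Two measures, kcal and grams of protein (sections 2.1.3 and 6.2.1).
- Level 5% (section 6.2.3). The number of sides is not stated; two-sided is assumed.
- About 60 residents (section 4.1), randomised 1:1 (section 3.3), so 60 / 2 = 30 per arm.
- Correlation between the two test statistics: not in the documents. It is an assumption, shown over a range.

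**Formulas, with no effect on either measure**
- Upper bound if either counts, at any correlation: 0.05 + 0.05 = 0.10.
- Independent tests: 1 − 0.95² = 0.0975.
- Correlated tests: P(either) = 1 − P(|Z₁| < 1.96 and |Z₂| < 1.96), with (Z₁, Z₂) bivariate normal.
- P(both) = 0.05 + 0.05 − P(either).
- P(exactly one) = P(either) − P(both).

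| Assumed correlation | Either | Both | Exactly one |
|---|---|---|---|
| 0 | 9.75% | 0.25% | 9.50% |
| 0.5 | 9.07% | 0.93% | 8.14% |
| 0.8 | 7.81% | 2.19% | 5.62% |
| 0.9 | 7.04% | 2.96% | 4.08% |
| 0.95 | 6.46% | 3.54% | 2.92% |
| 0.98 | 5.93% | 4.07% | 1.86% |

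**Check with the planned test.** In 40,000 simulated null trials per correlation, with 30 per arm and Wilcoxon tests using a continuity-corrected normal approximation, each single test rejected in 4.6% to 4.9% of trials. At least one rejected in 9.2%, 8.8%, 7.6%, 6.9% and 6.4% at data correlations 0, 0.5, 0.8, 0.9 and 0.95. The table is therefore a good guide at this sample size.

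**If both are required.** Two rejections cannot be more frequent than rejection by the measure with no effect, so the error rate stays at or below 5% whatever the correlation, and even if the other measure is truly affected.

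**Where in the range the trial would fall.** Both measures come from the same trays, which favours a positive correlation. The menu matching in section 5.1 (Step 2) adds nothing here. Its text, "The composition in macronutrients and in particular the caloric and protein contributions, will be identical and preserved", concerns each finger-food menu and its usual counterpart, so it equalises what the arms are offered; it does not make calories and protein move together within a resident. Section 2.1.3 also records which type of dish was eaten, and a resident who takes the dessert but leaves the meat would separate the two measures. Only the 10% bound is free of assumptions.

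**Which branch the text supports.** The Summary and sections 1.1, 2.1.3 and 6.2.1 all name calories and protein together, never as alternatives, and section 6.2.5 has one main criterion. That leans away from the branch with inflation, although it is not a stated rule.

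**The case for a change.** The strongest case for a change is that high correlation shrinks the inflation without removing it (5.93% even at 0.98), and that the missing decision rule matters at any correlation below 1. Disagreement is not far-fetched. Suppose each test had 50% power, an illustrative value since the documents give none. Then P(both) is about 1/4 + arcsin(ρ)/2π, or 0.398, 0.428 and 0.449 at ρ = 0.8, 0.9 and 0.95, and exactly one test is significant in 2 × (0.5 − P(both)), about 20%, 14% and 10% of trials. Section 1.1 itself reports an earlier hospital evaluation as positive on protein and mentions no caloric result. The pilot label is not a full answer either: section 1 speaks of verifying a hypothesis, section 1.2 of demonstrating benefits, and formal tests are planned. One sentence would settle the matter.

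Much of this stands. The arithmetic is right, and the text leaves the joint reading open. It does not carry the point to a needed change, for three reasons.

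- The inflation requires a success rule that the documents do not contain. The main objective is to evaluate, with no success threshold or go/no-go decision attached. The benefits listed in section 1.2 are nutritional status, autonomy, behaviour, quality of life and comorbidities, not intake.
- The ambition in section 1 is tempered by section 6.2.2 and by the Summary, which place formal hypotheses in a later study.
- No single remedy follows from the documents. Testing in a fixed order would rank two measures that section 1.1 treats as equals, and nothing says which comes first. Requiring both, halving the level, or calling both p-values exploratory are each defensible in an unpowered pilot, and statisticians would differ on the choice.

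**Conclusion.** No change to the plan is called for. There is a true gap: two primary measures, one unsplit 5% level, and no rule for reading them together. It is missing detail and a fair trade-off in a pilot, not an error. If the plan is followed, the test of calories is valid at 5% and so is the test of protein. A sensible analyst reports both and draws no overall conclusion from whichever looks better.

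The size depends on the reading. If either result counted, the overall error would be at most 10%, and between 5.93% and 9.75% for assumed correlations from 0.98 down to 0. If both had to succeed, it would be at most 5%. These figures assume two-sided tests and, apart from the two bounds, a correlation the documents do not supply.

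The judgement also rests on the text that was available: a short part just before section 6.2.1 was not, though the primary-endpoint paragraph itself is complete. It would change if the results were presented as a confirmatory claim resting on one of the two measures.

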#### Secondary endpoints :

The evolution of all the parameters collected throughout the monitoring will be described graphically.

#### Nutritional indicators :

The evolution of all nutritional indicators between inclusion and 6 months will be compared between the 2 groups by a Wilcoxon Mann-Whitney test.

#### Associated comorbidities:

The number of pressure sores/wounds and the number of falls will be compared between the 2 groups by a Wilcoxon Mann-Whitney test.

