#### 2.2.2 Secondary endpoints

All endpoints will be compared between the no "finger-food" period (M-1 - M0) and the resident follow-up period (M0 to M6) depending on the randomization arm.

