#### **Associated Comorbidities:**

- Number of wounds and pressure sores per month

New pressure ulcers and their severity will be plotted throughout the study.

- Number of falls per month

The number of falls will be plotted throughout the study.

These comorbidities will be extracted from the ennov software by a clinical research IDE.

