### 5.2 STUDY SCHEDULE

Actions		Inclusion	M-1 to M0	M0 to M1	M1 to M2	M2 to M3	M3 to M4	M4 to M5	M5 to M6
Collection of non-opposition Size measurement		X							
Randomization			х						
Collection of consumption: nutritional intake*.			х	х	х	x	х	х	x
Nutritional Indicators**			x	x	Х	Х	х	x	х
Nutritional Indicators***			Х						х
Associated comorbidities ****			Х	Х	Х	Х	Х	Х	Х
Autonomy	Power supply (EBS)		Х			Х			Х
Autonomy	GIR		Х						Х
Eating behavior (Blandford scale)			Х			x			х
Resident satisfaction (VAS of faces)			Х	Х	Х	X	Х	Х	x
Impact on professionnals			Х	Х	Х	X	Х	Х	x
Significant events on food intake *****			Х	Х	Х	Х	Х	Х	Х

\*3 consecutive days, for lunch and dinner, at a time t between M-1 and M0, then monthly

\*\*Weight, BMI \*\*\* Biological indicators (albumin/ pre-albumine/ CRP), MNA screening score \*\*\*\* Number of pressure score and severity, number of falls, infectious complications: over the entire study period \*\*\*\*\* Medical and environmental events, drug consumption, hospitalization (number, reasons, duration)

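### Falls and pressure sores are tested as raw counts with no window, time at risk or baseline term, so section 6.2.1 does not carry section 2.2.2 through and unequal exits would bias the comparison

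*Combined protocol and SAP*

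**What the plan says.** Section 6.2.1, under Associated comorbidities, gives the whole planned test in one sentence: "The number of pressure sores/wounds and the number of falls will be compared between the 2 groups by a Wilcoxon Mann-Whitney test". The neighbouring entries in 6.2.1 are worded differently. The nutritional one reads "The evolution of all nutritional indicators between inclusion and 6 months will be compared between the 2 groups by a Wilcoxon Mann-Whitney test", and those for autonomy, satisfaction and workload also test a change from inclusion to 6 months.

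Section 2.2.2 defines the two comorbidity endpoints as "Number of wounds and pressure sores per month" and "Number of falls per month". Its opening line sets up a comparison, for all secondary endpoints, of the no-finger-food "period (M-1 - M0) and the resident follow-up period (M0 to M6) depending on the randomization arm". The footnote to the schedule in section 5.2 says that these events are collected "over the entire study period"; the schedule has a column for M-1 to M0 and one for each month to M6.

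Three other rules decide what happens to a resident who leaves early. Section 6.2.7 analyses everyone included. Section 5.3.1 removes a resident from the study on request. Section 6.2.5 gives a missing-data rule for food intake only.

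**The concern.** A resident followed for two months has less opportunity to fall than one followed for six. The plan keeps both in the analysis, has no rule for a truncated count and names no denominator, so the short count enters the test as if it were complete. If one arm loses more residents or loses them earlier, its counts fall for that reason alone.

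The text also leaves the analysis undefined. Section 6.2.1 has a number, section 2.2.2 has a monthly number, and the opening of 2.2.2 sets one month against six, which makes sense only for rates. Nothing in 6.2.1 converts one into another, so several different analyses could each be called per protocol.

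Reduction of comorbidities is among the benefits that section 1.2 says the study seeks to show, and section 6.2.2 gives the purpose of the pilot as preliminary data. A rank-test p-value on truncated counts supplies neither a clean comparison nor an event rate for planning a later trial.

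**Working it through.** The plan states no power, event rate or exit rate for these endpoints, so there is no figure of its own to reproduce.

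**Inputs from the documents.** About 60 residents (4.1), allocated 1:1 (3.3), hence about 30 per arm; one month before M0 and six after (7 months of follow-up in the Summary); significance level 5% (6.2.3), taken as two-sided.

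**Assumptions, not in the documents.** Gamma-Poisson counts at 0.15 or 0.30 events per resident-month; gamma dispersion 1.0 in the main scenarios; constant exit hazard, unrelated to event risk; rate ratio 1.0 or 0.5.

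**Step 1: size of the bias.** With equal event rates, the ratio of mean counts equals the ratio of mean time at risk. If a share p has left by M6 at constant hazard, mean time at risk over the six months is T(p) = 6p / [−ln(1 − p)].

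- T(0.10) = 0.6 / 0.1054 = 5.69 months
- T(0.30) = 1.8 / 0.3567 = 5.05 months
- T(0.50) = 3.0 / 0.6931 = 4.33 months

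Exits of 10% v 30% give 5.05 / 5.69 = 0.89, an apparent 11% reduction. Exits of 10% v 50% give 4.33 / 5.69 = 0.76, an apparent 24% reduction. Simulation agrees: 0.89 to 0.90 and 0.74 to 0.77. Equal exits of 20% give a simulated ratio of 0.99 to 1.00.

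**Step 2: type I error** (1,500 runs per scenario, Monte Carlo standard error about 0.6 points; each cell shows 0.15 / 0.30 per month).

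| Exits | Wilcoxon, raw counts | Negative binomial with log-time offset |
|---|---|---|
| 20% v 20% | 5.5% / 5.1% | 6.1% / 5.7% |
| 10% v 30% | 5.2% / 6.7% | 5.2% / 5.5% |
| 10% v 50% | 9.6% / 12.1% | 5.1% / 5.5% |

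At 10% v 50%, nearly all rejections favour the arm with more exits. Separate runs put the raw-count figure there at up to about 14%. With less over-dispersion (0.5) at 0.30 per month, 600 runs gave 9.0% at 10% v 30% and 18.3% at 10% v 50%.

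**Step 3: power with balanced exits** (20% per arm, rate ratio 0.5, standard error about 1.3 points).

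| Analysis | 0.15/month | 0.30/month |
|---|---|---|
| Wilcoxon, raw counts | 27.5% | 34.9% |
| Wilcoxon, counts per month | 27.3% | 35.9% |
| Negative binomial, no offset | 34.5% | 45.2% |
| plus time offset | 34.7% | 47.2% |
| plus baseline-month count | 36.5% | 50.6% |

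Replacing the rank test by a count model adds 34.5 − 27.5 = 7.0 and 45.2 − 34.9 = 10.3 points. The offset adds 0.2 and 2.0, and the baseline month 1.8 and 3.4. The first gap is there with no exits at all (31.9% v 40.8%; 41.4% v 52.3%). Part of it reflects the count models' slightly high type I error: 6.9% and 7.4% for the full model at equal 20% exits.

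A separate check at 0.1 events per month (1,000 runs, quasi-Poisson) put the full model only about 2 points above the Wilcoxon test: 19.2% v 17.1%, and 25.3% v 23.8%.

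**The case against.** The strongest reply is that section 2.2.2 already handles this: it defines both endpoints per month and names the baseline period and the comparison by arm. That stands in part. A reader might infer that the protocol ignores rates and baseline altogether, and it does not. What remains is that the stated test in 6.2.1 uses neither.

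Second, a reader might infer that early exits will make finger-food look beneficial. That needs more exits in the finger-food arm. The trial is open, and section 5.1 foresees reluctance about eating with the fingers, so an imbalance is plausible, but the documents give no exit or death rates. More exits among controls would look like harm, and equal exits bias nothing.

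Third, a reader might infer that ignoring time at risk costs power even when exits are balanced. Step 3 does not support that: the offset is worth about 0 to 2 points at 20% exits.

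Fourth, a reader might take the footnote in 5.2 to put the month before finger-food into the tested count, which would turn a true ratio of 0.60 into (1 + 6 × 0.6) / 7 = 0.66. The footnote belongs to a collection schedule with separate monthly columns. It does not define an analysis window, so that dilution is not established.

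Finally, these are secondary endpoints under an objective worded as description, in a pilot without a power target. That limits the weight of the point.

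**Conclusion.** The point holds as a gap between sections 2.2.2 and 6.2.1. The stated test compares raw numbers with no window, exposure or baseline term, and truncated counts enter it uncorrected.

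The consequence is conditional: any imbalance in exits shifts the comparison in favour of the arm with more exits. At 10% v 30% exits the distorted estimate matters more than the modest change in type I error. Only at a large imbalance such as 10% v 50% does type I error clearly rise. These sizes rest on assumed event rates, dispersion and exit shares, and on exits unrelated to event risk, which is the simplest case.

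The power gain from the baseline month is modest and negligible at low event rates. Part of the remaining gap is rank test versus count model and should not be attributed to time at risk. The point is moderate and cheap to put right.

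**What to change.** In section 6.2.1, count new events from M0 to M6. Compare the arms, separately for falls and for new sores/wounds, with a negative binomial or over-dispersed Poisson model. Use log(time at risk, less hospital days) as offset and the M-1 to M0 count as covariate. Report the rate ratio with its 95% confidence interval. Include residence only if event numbers allow: in a check at 0.1 events per month, adding six residences raised type I error to 7.4 to 8.0%. Align section 2.2.2 with this window and model.

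Record exit and death dates, and report exits and deaths by arm. Hospital stays and their duration are already traced (2.2.2), but the text available does not expressly list exit or death dates.

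Copying the neighbouring entries by testing a per-month change with the Wilcoxon test would be a poor repair. One baseline month is noisy: in 600-run scenarios with 20% exits, power was 17 to 27%, against 25 to 52% for raw counts.

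The cost is a few lines of SAP text, one standard model per outcome and two date fields. The downsides are an over-dispersion assumption and a type I error that can be slightly high with sparse events. The offset also does not correct exits related to event risk, such as deaths among the frailest, which is a further reason to show exits and deaths by arm.
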